6.4. Study Visits Description and Procedures

A written, signed informed consent form (ICF) must be obtained from each subject prior to performing any study related procedure (*i.e.*, physical examination, clinical laboratory sampling, urine pregnancy test, ECG, or photography).

6.4.1. Visit 1/ Screening (Day -28 to 0)

At this visit, the investigator or designee will:

1. Review and explain the nature of the study to the subject, obtain the subject's signature on the appropriate approved ICF and provide a signed and dated copy to the subject.
2. Assign a SI to the subject.
3. Confirm the subject meets all inclusion criteria and no exclusion criteria.
4. Collect demographic and medical history information (including vitiligo history).
5. Collect concomitant therapies information.
6. Perform a physical examination.
7. Measure vital signs.
8. Conduct an ECG.
9. Collect blood samples for clinical laboratory tests including serum pregnancy test.
10. Quantify the facial vitiligo BSA involvement. The subject must have non-segmental facial vitiligo involving at least 0.25% TBSA (excluding the upper and lower eyelids, mucosal lip areas, and forehead and chin areas covered by the stereotactic positioning device) with at least one facial area with normal pigmentation.
11. Perform the Vitiligo Area & Scoring Index (VASI).
12. Review the study instructions with the subject.
13. Schedule Visit 2 as appropriate.

6.4.2. Visit 2 (Day 1) / Baseline

This visit must occur within 28 days after Visit 1.

Subsequent study visit dates must be scheduled based on the date of Visit 2.

This visit may not occur before the investigator reviews the Visit 1 clinical laboratory test results for all the measured analytes. For the subject to continue in the study all clinical laboratory test results must be within the range of normal for the laboratory or, if there are any abnormal results, they must be defined as not clinically significant (NCS) by the investigator. Subjects with any Screening laboratory values meeting the Study Medication Interruption Criteria found in Table 1 must have repeat lab testing performed with results meeting the minimum criteria for resumption in order to initiate treatment at Baseline (Visit 2). For WOCBP, the serum pregnancy test from Visit 1 must be negative for a subject to continue in the study.

The investigator must review the evaluator's interpretation of each subject's Visit 1 ECG prior to Baseline/Visit 2 and comment on the clinical significance of any result that is defined by the evaluator as abnormal. The subject must not continue in the study and apply study medication, if the Visit 1 ECG meets any of the Criteria in Exclusion Criterion 21.

At this visit, the investigator or designee will perform the following procedures **PRIOR TO APPLICATION OF STUDY MEDICATION:**

1. Query the subject in a non-directive manner about any changes in her/his health since the previous visit and report changes on the appropriate form.
2. Query the subject about any changes in her/his concomitant therapies since the previous visit and report changes on the appropriate form.
3. Confirm the subject continues to comply with all study requirements, is eligible to continue in the study and has followed all study instructions.
4. Confirm the subject meets all inclusion criteria and no exclusion criteria.
5. Confirm Facial vitiligo TBSA is at least 0.25% with at least one area of normal pigmentation on the face.
6. Measure vital signs.
7. Perform a urine pregnancy test for WOCBP; results must be negative for the subject to apply the first dose of study medication.
8. Quantify the facial vitiligo BSA involvement. The subject must have non-segmental facial vitiligo involving at least 0.25% TBSA (excluding: the area from the eyebrows to and including the upper eyelids, the area from the bony rim of the orbit to and including the lower eyelids; mucosal lip areas; and forehead and chin areas covered by the stereotactic positioning device) with at least one facial area with normal pigmentation.
9. Perform the Facial Vitiligo Area Scoring Index (F-VASI).
10. Perform the total body VASI.
11. Confirm subject is eligible to apply the first dose of study medication.
12. Have the subject perform a pre-application Local Tolerability Assessment (LTA).
13. The Investigator or designee will perform a pre-application LTA.
14. Collect blood samples for clinical laboratory tests.
15. Take standardized photographs.
16. Conduct an ECG.
17. Have the subject complete the VitiQoL.
18. Discharge from the study subjects who are not eligible to apply the first dose of study medication.

For subjects who are eligible to apply the first dose of study medication the investigator or designee will perform the following procedures:

1. Dispense study medication to the subject.
2. An investigational staff member will instruct the subject on the proper study medication application technique and will observe the subject's first study medication application.
3. A staff member will monitor the subject for at least 20 minutes after the first study medication application completion time to detect any adverse events.
4. Have the subject perform a post-application LTA 10 (± 4) minutes after the application completion time.
5. The investigator or designee will perform a post-application LTA 20 (± 4) minutes after the application completion time.
6. Review the study instructions with the subject.
7. Schedule Visit 3 as appropriate.

6.4.3. Visit 3-9 (Weeks 1, 2, 4, 8, 12, 16 and 20) These visits must occur on the following weeks after Visit 2:

- Visit 3, 1 week (± 4 days)
- Visit 4, 2 weeks (± 4 days)
- Visit 5, 4 weeks (± 4 days)
- Visit 6, 8 weeks (± 4 days)
- Visit 7, 12 weeks (± 4 days)
- Visit 8, 16 weeks (± 4 days)
- Visit 9, 20 weeks (± 4 days).

At these visits, the investigator or designee will perform the following procedures:

1. Query the subject in a non-directive manner about any changes in her/his health since the previous visit and report all AEs on the appropriate form.
2. Query the subject about any changes in her/his concomitant therapies since the previous visit and report changes on the appropriate form.
3. Confirm the subject continues to comply with all study restrictions, is eligible to continue in the study and has followed all study instructions.
4. Measure vital signs.
5. **AT VISIT 3, 5-9, ONLY** collect blood samples for clinical laboratory tests.
6. **AT VISIT 3, 5-9, ONLY** conduct an ECG.
7. **AT VISIT 3-9**, Have the subject perform an LTA.
8. **AT VISIT 3-9**, The investigator or designee will perform an LTA.
9. **AT VISITS 5-9 ONLY**, perform the F-VASI
10. **AT VISIT 7 ONLY**, perform the total body VASI.
11. **AT VISIT 5-9 ONLY**, have the subject complete the Vitiligo Noticeability Scale (VNS).
12. **AT VISIT 7-9 ONLY**, have the subject complete the VitiQoL.
13. **AT VISITS 5-9, ONLY** perform a urine pregnancy test for WOCBP; results must be negative for the subject to continue in the study.
14. **AT VISIT 7-9 ONLY**, have the subject complete the Subject Vitiligo Satisfaction Scale (SVSS).
15. **AT VISITS 5-9 ONLY**, take standardized photographs.
16. Dispense and/or collect study medication as appropriate.
17. Review the study instructions with the subject.
18. Schedule the next visit as appropriate.

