³ Vitals signs include: oral or ear temperature, blood pressure, heart rate, respiration rate (height and weight at screening only).											
⁴ Clinical laboratory sampling include: CBC, Chemistry with lipids, and Urinalysis. Quantiferon Gold, HIV, Hepatitis B and C, TSH, T3, Free T4 and Serum Pregnancy should be done at screening visit only. Subjects with any Screening laboratory values meeting the Study Medication Interruption Criteria found in Table 1 must have repeat lab testing performed with results meeting the minimum criteria for resumption in order to initiate treatment at Baseline (Visit 2).											
⁵ UPT must be performed in WOCBP prior application of study medication at Baseline (Visit 2) and must be negative for the subject to continue in the study. UPTs in WOCBP must also be obtained at Visit 5, 6, 7, 8, 9, 10, and 11. WOCBP must have a negative serum pregnancy test at Screening (Visit 1) and a negative UPT at baseline (Visit 2) prior to application of study medication.											
⁶ F-VASI must be determined at Baseline (Visit 2) and Visits 5-11. During the baseline visit, F-VASI should be determined prior to application of study medication.											
⁷ Canfield photography will be performed at Prior to dosing at Baseline (Visit 2) and at Visits 5, 6, 7, 8, 9, 10 and 11.											
⁸ Subjects will complete the Subject Vitiligo Satisfaction Scale at Visits, 7, 8, 9, and 10 and at post-treatment Visit 11.											
⁹ The study staff must instruct the subject to apply study medication according to the instructions in APPENDIX 1.											
¹⁰ The study staff must weigh the study medication bottle(s) with cap prior to dispensing to the subject and after the study medication bottles are returned to the investigational site. Staff should review the usage based on the weight of the bottle and counsel the subject as necessary.											
¹¹ At Baseline (Visit 2), the first application of study medication should be performed by the subject under the supervision of the study staff and the subject should be observed for 20 minutes after the initial application.											
¹² A written, signed ICF with the additional visits (Visits 12 -15) must be obtained from each subject prior to performing any Visit 12 study related procedure.											
¹³ For subjects who consent to continue for additional study visits, Visit 12-15, study medication should be dispensed.											

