8.2.1. ECGs

Standard 12-lead ECGs will be performed by a qualified staff member at Screening (Visit 1), Baseline (Visit 2), Day 8 (Visit 3), Visits 5-10, Visit 11 (if applicable) and if continuing for the additional visits, Visit 15. The ECGs must be obtained using a standard 12-lead ECG with a 10mm/mV amplitude, at 25mm/sec and a 5-10-second duration. To ensure a steady heart rate the subject must rest quietly in the supine position for at least 5 minutes prior to performing the ECG.

A central lab, eResearchTechnology, Inc. (ERT), will provide ECG equipment, supplies and site training. In addition, ERT will process ECGs received by the sites and report results via a secure study portal. The ECG results will be interpreted by a qualified health professional (evaluator) and the interpretation reported either directly on the tracing or in a separate report. The evaluator will interpret the results of every ECG and define the ECG as “normal” or “abnormal”. Variations such as minor ST changes (*i.e.*, <0.5mm depression) and early re-polarization are considered normal.

The investigator must review the evaluator’s interpretation of each subject’s screening ECG prior to Baseline (Visit 2). The investigator will review, sign and date the evaluator’s interpretation of all ECG reports in a timely manner and comment on the clinical significance of any result that is defined by the evaluator as abnormal.

Any abnormalities that are, in the opinion of the investigator, clinically significant, must be reported as history if found prior to the start of the first study medication application or as an AE if found after the start of the first study medication application (see Section 9.1.1).

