8.2.4. Clinical Laboratory Assessments

At the visits detailed in the Schedule of Assessments, a qualified staff member will collect non-fasting samples for clinical laboratory analysis. Approximately 18.5 ml of blood will be collected at Visit 1 and approximately 10.5 ml for each sample detailed in the Schedule of Assessments a total of approximately 113 ml per subject for Visit 1-11, approximately 42 ml for Visits 12-15, and up to approximately 155 ml for the entire study. Samples will be sent to a central laboratory for analysis. Refer to the study specific laboratory manual for handling and shipping instructions. The following tests will be conducted:

Chemistry Panel	Complete Blood Count
Albumin	Hematocrit
Alkaline phosphatase	Hemoglobin
Alanine aminotransferase (ALT)	Platelet count
Aspartate aminotransferase (AST)	Red blood cell morphology
Blood urea nitrogen (BUN)	Red blood cell count
Bicarbonate	White blood cell count
Calcium	White blood cell differential
Chloride	% & absolute
Creatinine	Basophils
Glucose	Eosinophils
Lactate dehydrogenase (LDH)	Lymphocytes
Phosphorus	Monocytes
Potassium	Neutrophils
Sodium	
Total bilirubin	
	Urinalysis

Total protein
Uric acid
Total cholesterol, LDL, HDL,
Triglycerides
CPK
Screening Only
Virology (HepB, HCV, HIV)
Quantiferon Gold
T3/T4, TSH
Serum pregnancy

The results of the clinical laboratory tests will be reported on the central laboratory's standard reports. The investigator must note NCS or CS to define the clinical relevance of any result that is outside the normal range for the laboratory. The investigator must date and initial every laboratory report.

The investigator or subinvestigator must review all the Screening (Visit 1) laboratory test results against the study entry criteria for each subject prior to Baseline (Visit 2). The investigator must report all laboratory results that are BOTH outside the normal range for the laboratory AND, in the opinion of the investigator, CS as medical history if found prior to the first study medication treatment or as an AE if found after the first study medication treatment begins. The investigator must review all laboratory reports in a timely manner.

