9.1. Definitions

9.1.1. Adverse events (AE)

An AE is any untoward medical occurrence in a subject administered a study medication(s) and which does not necessarily have a causal relationship with the study medication. An AE can therefore be any unfavorable and unintended sign or symptom associated with the use of a study medication (including an abnormal laboratory finding), whether or not related to the study medication.

Thus, any new, clinically significant worsening of an existing sign, symptom or disease, should be considered an AE.

Every new episode or clinically significant worsening of a chronic condition (e.g., headaches, seasonal allergies, depression, or hypertension) should be reported as a separate AE, even if the condition is reported in the subject's medical history.

The investigator should, when certain, report a diagnosis rather than the signs, symptoms or clinically significant abnormal laboratory values associated with the AE. Otherwise, signs, symptoms or abnormal laboratory values may be used to describe the AE.

Any CS abnormality discovered prior to the first study medication treatment should be reported as medical history, not as an AE.

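### Read literally, a new clinically significant abnormality on the pre-dose Visit 2 blood sample is filed as an adverse event, because the rule goes by when it is found, not when the sample was taken

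*Combined protocol and SAP*

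**What the plan says.** Section 6.4.2 opens the Visit 2 procedures with "At this visit, the investigator or designee will perform the following procedures PRIOR TO APPLICATION OF STUDY MEDICATION". Step 11 in that list is "11. Confirm subject is eligible to apply the first dose of study medication"; the blood draw ("14. Collect blood samples for clinical laboratory tests") and the ECG ("16. Conduct an ECG") come after it. The first dose is given at the same visit: under the Section 6.3 footnotes, "the first application of study medication should be performed by the subject under the supervision of the study staff".

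Section 8.2.4 sends blood to a central laboratory. It requires Visit 1 results to be reviewed before Visit 2, and other reports only in a timely manner. Section 8.2.1 does the same for ECGs: the screening tracing must be reviewed before Visit 2, and a central vendor processes the tracings, but the interpretation may be written on the tracing itself.

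Three sections say how a clinically significant abnormality is filed:

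- Laboratory (8.2.4): "as medical history if found prior to the first study medication treatment or as an AE if found after the first study medication treatment begins".
- ECG (8.2.1): it "must be reported as history if found prior to the start of the first study medication application or as an AE if found after the"; the sentence ends by naming that same application as the dividing point.
- General (9.1.1): "Any CS abnormality discovered prior to the first study medication treatment should be reported as medical history, not as an AE".

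Section 9.1.1 also defines an AE as an untoward occurrence in a subject who has been given study medication. Section 11.2 tabulates the proportion of subjects with treatment-emergent AEs. The abbreviation list expands that term, but no section gives an onset rule for it.

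**The concern.** The filing rule depends on when someone learns of the abnormality, not on when the blood was drawn or the tracing recorded. For most visits the two fall on the same side of the first dose. Visit 2 is the exception: the sample is taken before any drug is applied and the result is seen afterwards. A site that follows Section 8.2.4 to the letter must enter a clinically significant finding from that sample as an AE, and must then rate its relationship to the drug under Section 9.1.6, although the subject had received none when the sample was taken.

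Safety is part of the primary objective (Section 4.1), and the study has a single arm, so no comparison group would show the same misfiling and offset it. With about five sites, some may follow the wording and others may file by sample time, which would make the AE data inconsistent between sites.

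**Working it through.** **Is the Visit 2 sample a planned central-laboratory draw?** Section 6.3 schedules laboratory draws at Visits 2, 3 and 5 to 11 (nine samples) and at Visits 12 to 15 (four). Section 8.2.4 gives 18.5 mL at Visit 1 and 10.5 mL per later sample.

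- Visits 1 to 11: 18.5 + 9 × 10.5 = 113 mL
- Visits 12 to 15: 4 × 10.5 = 42 mL
- Total: 113 + 42 = 155 mL

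All three match the stated volumes, and the nine samples include Visit 2.

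**Does the result gate the first dose?** No. Eligibility is confirmed at step 11, blood is drawn at step 14 and the ECG is done at step 16. Only Visit 1 laboratory results and the Visit 1 ECG must be reviewed beforehand. The plan does not wait for the central laboratory, so in practice the Visit 2 laboratory report is read after the first application. For the ECG the documents leave the order open.

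**Where does a clinically significant finding go?**

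| Finding | Sample or tracing taken | Result seen | Filed under 8.2.1 / 8.2.4 |
|---|---|---|---|
| Visit 1 laboratory or ECG | before dose | before dose | history |
| Visit 2 laboratory | before dose | after dose | AE |
| Visit 2 ECG, read on site first | before dose | before dose | history |
| Visit 2 ECG, read later | before dose | after dose | AE |
| Later visits | after dose | after dose | AE |

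Rows two and four conflict with the AE definition in Section 9.1.1.

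**Does a later step remove it?** Not as written. Non-serious AE reporting starts with the first application (Section 9.1.4), but Section 11.2 gives no onset rule. The sample and first dose share Day 1, so a derivation that compares dates only could not tell them apart.

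**Size.** One subject out of 33 is 1/33 = 3.0 percentage points of the AE proportion, if that subject has no other AE. The documents give no rate *p* for a new clinically significant finding on the Visit 2 pre-dose tests, so a range is assumed. Expected number misfiled = 33 × *p*; chance of at least one = 1 − (1 − *p*)^33.

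| Assumed *p* | Expected of 33 | Chance of at least one |
|---|---|---|
| 1% | 0.33 | 28% |
| 3% | 0.99 | 63% |
| 5% | 1.65 | 82% |
| 10% | 3.3 | 97% |

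**The case against.** The best reply is that the protocol, read as a whole, points the other way. The AE definition presupposes a subject who has been given drug, Section 9.1.1 refers to new or worsening conditions, and Section 9.1.6 asks the investigator to weigh timing when judging causality. A sensible investigator would take *found prior to* as found on a pre-dose test. That may well happen, but Section 8.2.4 words the rule as mandatory and keys it to finding. The conflict remains, and nothing in the plan says which text prevails.

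The reply does limit the point in several ways.

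- A reader might infer that the Visit 2 ECG is always read after dosing. The documents do not support that, because Section 8.2.1 allows the reading on the tracing.
- A reader might infer that every pre-dose abnormality becomes an AE. The rule covers only those judged clinically significant. Section 6.4.2 lets a subject continue only if Visit 1 laboratory results, at most 28 days old, are normal or not clinically significant. What is left is findings that are new or have worsened since screening.
- A reader might infer that such an event is certain to be counted as treatment-emergent. That is undefined rather than settled.
- A reader might scale up from the panel: 22 chemistry and 10 blood-count analytes in 33 subjects give 32 × 33 = 1,056 results. Turning that into a number of subjects needs an out-of-range rate and a clinical-significance rate that the documents do not give. It would also ignore the Visit 1 screen and the clustering of related analytes within a subject.

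The by-visit tables will also show the value at Visit 2, so a careful reader could see that the abnormality was present before dosing. That helps interpretation but does not correct the AE count.

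**Conclusion.** The point holds for Visit 2 laboratory results, and for the Visit 2 ECG only when it is not read before application. Followed as written, the rule files a new clinically significant pre-dose finding as an AE, against the protocol's own AE definition, and no stated derivation takes it out again.

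The effect is at most 3.0 percentage points for each affected subject; it is smaller or nil in the overall proportion if that subject has another AE. How many subjects are affected cannot be derived from the documents. The 0.3 to 3.3 range rests entirely on assumed per-subject rates of 1% to 10%. The error inflates the AE proportion and touches no efficacy result. It merits correction because safety is part of the primary objective, the study is uncontrolled and small, and the remedy is simple.

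**What to change.** In Sections 8.2.1, 8.2.4 and 9.1.1, classify a clinically significant abnormality by whether the sample or tracing was taken before or after the first application. State that Visit 2 pre-application laboratory and ECG results are baseline, and that a clinically significant finding on them goes to medical history whenever the report arrives. In Section 11.2, define treatment-emergent as onset, or worsening from the pre-application state, after the first application. For Day 1, the derivation should use the pre-application status of the test and not the calendar date alone. Serious events should stay under Section 9.1.4, which starts their reporting at consent.

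The cost is a short wording change and a site memo, with no added procedure. No section says that collection times are recorded, so the sponsor should confirm that Visit 2 samples and tracings are identified in the data as pre-application; Section 6.4.2 already requires them to be taken then. One side effect should be noted: the AE follow-up duties in Section 9.2.1 do not attach to a finding filed as history.

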6.4.4. Visit 10 (Week 24)

This visit must occur 24 weeks (± 4 days) after Visit 2.

At this visit, the investigator or designee will perform the following procedures:

1. Query the subject in a non-directive manner about any changes in her/his health since the previous visit and report all AEs on the appropriate form.
2. Query the subject about any changes in her/his concomitant therapies since the previous visit and report changes on the appropriate form.
3. Confirm the subject continues to comply with all study restrictions and has followed all study instructions.

4. Measure vital signs.
5. Conduct an ECG.
6. Collect blood samples for clinical laboratory tests.
7. Perform a urine pregnancy test for WOCBP.
8. Have the subject perform an LTA.
9. The investigator will perform an LTA.
10. Perform the F-VASI.
11. Perform the total body VASI.
12. Have the subject complete the VNS.
13. Have the subject complete the SVSS.
14. Have the subject complete the VitiQoL.
15. Collect all study medication.
16. Take standardized photographs.
17. Review the study instructions with the subject.
18. For subjects who agree to continue to participate in additional study visits (Visits 12-15):
 - a. Obtain consent for additional study visits, Visit 12-15:
 - b. Dispense study medication.
 - c. Review study instructions with the subject.
19. Schedule Visit 12. For subjects who do not consent to continue with additional study visits (Visit 12-15), schedule the next visit, Visit 11.

